### **3.5 HLA Typing**

HLA subtypes will be determined using sequenced based typing methodology. Sequence based HLA-typing will be performed using the Histogenetics genotyping service which implements rigorous genotyping quality control assured by built-in redundancies. State-of the art software and bioinformatic tools will be utilized in sequence alignment and allele identification.

### **3.6 Statistical analysis**

Protocol V17 07.02.2023

At present, we are unable to provide a total sample size of patients to be recruited. Given the different adverse drug reactions and the different frequencies at which they occur, it is not possible to give an exact number. However, given the rarity of some of the reactions, in most cases it will be unlikely that we will recruit more than 100 cases per culprit drug. Our general target will be 100 cases for each reaction.

For patients receiving oncological immunotherapy we will initially aim to recruit approximately 10 patients per drug to the cohort study and 25 cases and 25 controls per drug to the case-control study; however the study will institute a Bayesian inference with regard to sample size, using it to adjust the sample size within a dynamic analytical approach to the data analysis. Thus, we will recruit up to but no more than 100 patients (who complete the study) per drug as per the original protocol.

Given our case target it is vital we recruit patients both locally and nationally. As we are unable to state the exact number of patients to be recruited, we will provide figures for the number of patients recruited following an ADR for all the drugs that are studied to the ethics committee in the annual report.

### **3.7 Study endpoints:**

- Chemical characterisation of protein haptentation.
- In response to exposure to suspect drug, the degree of:
  - lymphocyte proliferation
  - cytokine secretion
  - change in cell surface marker expression
  - antibody release
  - changes in microbiota
- Identification of genetic / genomic/ transcriptomic factors as biomarkers of hypersensitivity

### **3.8 Pharmacokinetic sub-study**

Plasma drug levels will be determined using enzyme-linked immunosorbent assay (ELISA) or electrochemiluminescent (ECL) assays. For the case-control study, plasma will be taken from patients, but because they will present at different times, it may not always be possible to detect drug levels. The data from the prospective and case-control studies will be combined to develop a model to determine the relationship between dose and irAE. Analysis of specific cytokines, including but not limited to TNF, IL6, IL17, and IL23 in subsequent samples taken for PK analysis will be undertaken to inform the systems pharmacology knowledge base of immunotherapies.

Protocol V17 07.02.2023

## **4. Selection, Recruitment and Withdrawal of Participants**

### **4.1 Participant Selection**

#### **4.1.1 Case Control study – Drug Class NOS**

##### *Inclusion Criteria for Case-Control Studies (Adult)*

###### *Case (Age $\geq 18$ years):*

- a. Subject is willing to take part
- b. 18 years or over
- c. Diagnosis of drug hypersensitivity as per criteria laid out by the Phenotype Standardization Project. or clinician decision
- d. Written informed consent obtained

###### *Control groups 1 and 2:*

- a. Participant willing to take part
- b. Currently taking the drug in question without adverse reactions (Control group 1)
- c. Healthy volunteers who may or may not have been exposed to paradigm drugs/ chemicals without ADRs (Control group 2)
  
- d. Ethnically matched to the index patient
- e. Written informed consent obtained

##### *Exclusion Criteria for Adult Case-Control Studies*

- a. Unwilling to take part
- b. Subject is unable to consent
- c. Subject is, in the opinion of the Investigator, not suitable to participate in the study.

##### *Inclusion Criteria for Case-Control Studies (Paediatric)*

###### *Case (Age $< 18$ years):*

- a. Family are willing to take part
- b. Age less than 18 years at time of the recruitment
- c. Age 5 years or over at time of recruitment

Protocol V17 07.02.2023

- d. Diagnosis of drug hypersensitivity as per criteria laid out by the Phenotype Standardization Project. or clinician decision
- e. Written informed consent obtained
- f. Assent from older participants (judged on a case by case basis)

*Control groups 1 and 2:*

A control for the paediatric study may either be a paediatric or adult patient

- a. Participant/family willing to take part
- b. Currently taking the drug in question without adverse reactions (Control group 1)
- c. Healthy volunteers who may or may not have been exposed to paradigm drugs/ chemicals without ADRs (Control group 2)
  
- d. Ethnically matched to the index patient
- e. Written informed consent (and assent if older paediatric participant) obtained

*Exclusion Criteria for Paediatric Case-Control Studies*

- a. Unwilling to take part (or older participant unwilling to assent)
- b. Subject is, in the opinion of the Investigator, not suitable to participate in the study.

**4.1.2 Case-Control Study- Oncological treatments**

*Inclusion Criteria for Case-Control Studies*

Case (Age  $\geq$ 18 years):

- a. Subject is willing to take part
- b. 18 years of age or over
- c. Diagnosis of drug hypersensitivity, defined as any grade 2 irAE with a requirement for steroid treatment/ recurrence of symptoms/ >1 break in treatment OR grade 3/4 irAE, as per criteria laid out in the NCI CTCAE (v4) OR clinician decision OR an endocrinopathy of any NCI CTCAE grade
- d. Administration of at least one dose of either monotherapy or combination oncological treatment (including CPI, targeted treatments and chemotherapy)
- e. Any AE experienced up to 24 months after commencement of treatment
- f. Written informed consent obtained

*Control (Age  $\geq$ 18 years):*

Controls will be matched for age and duration of treatment to cases

- a. Participant willing to take part
- b. Currently taking oncological treatments without AE (grade 1 toxicity is acceptable)  
or

Protocol V17 07.02.2023

- c. Previously received oncological treatment, did not have >grade one toxicity and have stopped for reasons other than toxicity
- d. Ethnically matched to the index patient
- e. Written informed consent obtained

*Exclusion Criteria for Case-Control studies*

- a. Unwilling to take part
- b. Subject is unable to consent

Subject is, in the opinion of the investigator, not suitable to participate in the study

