## **2. Study Rationale, Objectives and Design**

### **2.1 Rationale**

Drug and chemical hypersensitivity remains a major clinical problem in the UK and USA. Methods for diagnosis of drug hypersensitivity are currently only available for penicillins but not for other drugs. Moreover, current methods for diagnosing penicillin hypersensitivity appear to have low sensitivity and specificity. It is, therefore, important to develop an assay that exhibits high sensitivity and

Protocol V17 07.02.2023

specificity to confidently diagnose drug hypersensitivity. The mechanistic studies described herein may help to identify novel diagnostic reagents for drug hypersensitivity, and provide valuable information that will further our understanding of hypersensitivity reactions with the potential for the development of novel diagnostic assays.

Immune related adverse events (irAE) are having a significant impact on cancer patients who are receiving checkpoint inhibitor (CPI) immunotherapy as part of their oncological treatment. These drugs cause novel toxicities. The constellation of irAEs includes colitis, hepatitis, endocrinopathies, pneumonitis, nephritis and dermatitis. irAEs clinically mimic autoimmune diseases (AID), in which CTLA-4 and PD-1/PDL1 has an established role, and can be severe, permanent and multi-organ effecting. National Cancer Institute Common Terminology Criteria for Adverse Events (CTCAE) Grade 3/4 irAEs are apparently indication-independent and seen in 5-30% (monotherapy) to ~55% (combination therapy) of patients. Insight into the immune processes involved in toxicity will inform further research, further drug design, reduce toxicity induced morbidity and optimise patient management and outcomes.

By nature of their mechanism of action, oncological treatments other than CPIs can also result in profound toxicities. In particular targeted treatments and cytotoxic agents disturb pathways fundamental to epithelial homeostasis, resulting in cutaneous toxicities including but not limited to folliculitis, vitiligo, bullous pemphigoid, non-specific maculopapular rashes and alopecia. Such toxicities can impair patients' quality of life and negatively affect clinical decision-making, which can result in early treatment cessation. Indeed, many of these treatments are increasingly being utilised in conjunction with CPIs supporting the need for better insight into the on and off target effect of these treatments.

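### Oncology controls are screened on any toxicity above grade 1 while cases are defined mainly by immune-related events, so the contrast can pick up non-immune differences; a grade 1 endocrinopathy also fits both groups

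*Protocol*

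**What the plan says.** All the operative criteria are in Protocol section 4.1.2.

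- **Cases, criterion c.** Hypersensitivity is "defined as any grade 2 irAE with a requirement for steroid treatment/ recurrence of symptoms/ >1 break in treatment OR grade 3/4 irAE", and the alternatives are "OR clinician decision OR an endocrinopathy of any NCI CTCAE grade". Nothing limits other toxicity in a case.
- **Controls, criterion b.** "Currently taking oncological treatments without AE (grade 1 toxicity is acceptable").
- **Controls, criterion c.** "Previously received oncological treatment, did not have >grade one toxicity and have stopped for reasons other than toxicity".
- **Treatments in scope (case criterion d).** "Administration of at least one dose of either monotherapy or combination oncological treatment (including CPI, targeted treatments and chemotherapy").
- **Matching.** "Controls will be matched for age and duration of treatment to cases"; control criterion d adds ethnicity. Non-immune toxicity is not a matching factor.

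Other sections describe the controls differently. Section 2.4.1.2 wants treated patients who show no toxicity, again without an immune qualifier. Section 5.1 calls them tolerant of the drug and free of hypersensitivity, and Appendix 3 (case-control schedule, Day 0) calls them non-hypersensitive. Section 3.3 gives the autoantibody comparison as patients with irAEs against patients without.

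**The concern.** In a case-control comparison, the controls should come from the treated population that produced the cases and should differ from them in the event that defines a case. Here the case event is immune-related, or at least a hypersensitivity reaction, but the control screen covers adverse events in general. Section 2.1 says of the other oncology drugs: "In particular targeted treatments and cytotoxic agents disturb pathways fundamental to epithelial homeostasis". Toxicity above grade 1 without an irAE is therefore foreseeable in the population that section 4.1.2 admits.

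If such patients are kept out of the control group while cases may carry any amount of the same toxicity, the groups differ in general tolerance of treatment as well as in irAE status. A cytokine, cell-surface, microbiome or transcriptomic marker that tracks non-immune toxicity could then separate the groups without any link to irAEs. The model of dose against irAE in section 3.8 draws on the case-control data and is exposed in the same way, if higher exposure brings more toxicity and so removes controls.

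Analysis could not easily repair this. Under the literal criteria no control has an event above grade 1, so there is no overlap on that variable to adjust within. The only remedy left would be to restrict the cases. The CRF list in Appendix 7 does not name an all-cause adverse event grade.

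**Working it through.** **1. The criteria applied to typical patients**

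| Patient | Case under 4.1.2? | Control under 4.1.2, read literally? | Control under 5.1 and Appendix 3? |
|---|---|---|---|
| A: checkpoint inhibitor plus chemotherapy, grade 2 event that is clearly cytotoxic, no irAE | No, unless by clinician decision | No | Yes |
| B: as A, plus a grade 3 irAE | Yes | No | No |
| C: grade 1 endocrinopathy, nothing else | Yes (any grade qualifies) | Yes (grade 1 is acceptable) | Unclear |

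A and B share the same non-immune event, but only B can enter the comparison. C fits both groups. Criterion b says AE and criterion c says toxicity, so c arguably covers only drug-attributed events. That still includes cytotoxic and targeted-drug effects.

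**2. The plan's own figure**

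Section 3.6 starts with 25 cases and 25 controls per drug. It gives no alpha, power, effect size or SD, so the figure cannot be reproduced, and this point does not dispute it. It serves below only as a group size.

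**3. Illustration with a binary marker (all inputs assumed)**

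Suppose a marker unrelated to irAEs is present in 20% of patients without, and 40% of patients with, a non-immune event above grade 1. Let p be the share of treated patients with such an event.

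Prevalence in cases = 0.2(1 − p) + 0.4p. Prevalence in screened controls = 0.2 (odds 0.25).

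- p = 0.3: 0.26; odds 0.26/0.74 = 0.351; odds ratio 0.351/0.25 = 1.4
- p = 0.5: 0.30; odds 0.30/0.70 = 0.429; odds ratio 1.7
- p = 0.7: 0.34; odds 0.34/0.66 = 0.515; odds ratio 2.1

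The true odds ratio with irAE status is 1.0 in each row.

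**4. Illustration with a continuous marker (all inputs assumed)**

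Let the marker shift by s SD in patients with a non-immune event above grade 1. The share of such patients is q in cases and 0 in controls. Then:

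- spurious difference d = q·s
- average variance v = [1 + q(1 − q)s² + 1]/2
- z = d / √(2v/n), with n per group
- chance of p < 0.05 (two-sided) = Φ(z − 1.96) + Φ(−z − 1.96)

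For q = 0.4, s = 1.0, n = 25: d = 0.4, v = 1.12, standard error √(2 × 1.12/25) = 0.299, z = 1.34, chance 27%.

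| q | s = 0.5 | s = 1.0 | s = 1.5 |
|---|---|---|---|
| 0.2 | 6% | 10% | 16% |
| 0.4 | 11% | 27% | 47% |
| 0.6 | 18% | 52% | 81% |

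(25 per group; nominal 5%.)

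Larger samples do not help, because d does not depend on n. For q = 0.4 and s = 1.0:

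- 50 per group: standard error √(2.24/50) = 0.212, z = 1.89, chance Φ(−0.07) = 47%
- 100 per group: standard error √(2.24/100) = 0.150, z = 2.67, chance 76%

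The cap of 100 per drug in section 3.6 corresponds to 50 per group if it counts both groups, and to 100 per group if it counts cases only.

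**5. With one rule for both groups**

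If q is the same in cases and controls, d = 0 and the chance returns to 5%. This requires that non-immune toxicity is not itself associated with irAE status.

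**The case against.** **The words may be shorthand.** Case criterion e reads "Any AE experienced up to 24 months after commencement of treatment", where the qualifying event is evidently meant. Section 2.4.2.2 introduces irAEs and then contrasts patients who do and do not experience toxicity. Section 5.1 and Appendix 3 describe controls as non-hypersensitive. If AE in section 4.1.2 means irAE, no selection on non-immune toxicity was intended. This stands as a possible reading. However, a site screens on the eligibility text, and that text does not say so.

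**Some of the excluded patients are not natural controls.** A reader might infer from section 2.1 that patients with alopecia or folliculitis are non-immune controls wrongly turned away. The documents do not support that. Section 5.3.2 takes samples from those same reactions in order to study immune activity around the hair follicle, and it covers skin hypersensitivity after any drug. Such a patient may be a case by clinician decision. Keeping these patients out of the controls is defensible.

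**Strictly tolerant controls protect the reference group.** If patients with grade 2 or higher rash, diarrhoea or raised liver tests became controls whenever a site called the event non-immune, misclassified irAEs would enter the reference group and dilute the contrast. Section 5.3.4 itself calls the mechanisms of hepatotoxicity largely unclear. This argues against admitting non-immune events of every kind. It does not argue against admitting the clear ones.

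**There is partial mitigation.** Appendix 3 records disease status, therapeutic history and medications, so disease burden can be addressed in analysis. The oncology cohort study samples patients before treatment and at toxicity, which allows within-patient comparisons that do not depend on these controls. Neither changes the case-control contrast itself.

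**Conclusion.** The asymmetry is in the current eligibility text, and sections 2.4.1.2, 4.1.2, 5.1 and Appendix 3 do not agree on who a control is. Read literally, the criteria select controls for low non-immune toxicity, and this can produce differences unrelated to irAEs. The grade 1 endocrinopathy overlap follows from the wording alone and needs no assumption.

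Two stronger conclusions are tempting and are not supported. The first is that markers will differ between the groups for this reason. That requires a marker linked to non-immune toxicity and a material share of cases with such toxicity, and the documents give neither. The second is that the odds ratios of 1.4 to 2.1, or the false-positive chances of 6% to 81%, estimate the bias in this study. They rest wholly on assumed inputs and show only how the bias would behave.

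The actual size cannot be determined from the documents. It is probably small for checkpoint inhibitor monotherapy, which together with PD-1/CTLA-4 combinations is what section 5.1 describes. It is probably larger where chemotherapy or targeted drugs are given, as section 4.1.2 allows.

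**What to change.** Reconcile sections 2.4.1.2, 4.1.2, 5.1 and Appendix 3 so that a control is defined by absence of the case event:

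- no adverse event above grade 1 that is, or could be, immune-related or a hypersensitivity reaction under study;
- no endocrinopathy of any grade, which removes the overlap with case criterion c;
- treatment not stopped because of such an event.

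Patients whose only events above grade 1 are clearly non-immune may then be controls. Record adverse events above grade 1, with grade and judged cause, in both groups, so that the comparison can be adjusted for them or repeated as a sensitivity analysis.

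The cost is an amendment to the control criteria, matching wording in three other places, and a CRF item. The control pool widens. The downside is that sites must judge immune-relatedness in controls, with some risk of misclassification. Excluding doubtful events limits that risk but leaves a smaller asymmetry, because cases may still carry such events. The recorded data would show how large it is.

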#### *Control Group*

- Cases and controls will be recruited in a 1:1 manner
- Only one group of controls (patients receiving the drug but not exhibiting toxicity) will be recruited for this section
- Controls will be required to be receiving treatments for a minimum period outlined in the eligibility section

Due to the very limited use of oncological immunotherapies in children, only adults will be recruited to this arm of the case control study.

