Storage in liquid nitrogen to restimulate responding T cell lines and clones as and when required. Adult patients that produce the most vigorous response in the lymphocyte transformation test (LTT) may be asked to donate further blood samples; the patients that are re-called will be asked to donate up to 60mL of venous blood. We believe it is important to make these patients aware of the LTT result to their medication(s), so that severe reactions can potentially be avoided in the future. Paediatric patients will be assessed on a case by case basis. Any further requests for blood samples will be guided by the EMA guidelines (and the wishes of the patient/family) but will not exceed 3% total circulating volume in a 4-week period (approx. 2.4ml/kg).

For patients taking oncological immunotherapies, those displaying hypersensitivity and those tolerant to the drug will both be recruited. The samples provided by this control patient cohort who do not display hypersensitivity will act as experimental controls. Patients receiving PD-1 inhibitor monotherapy or in combination with a CTLA-4 will be recruited into the study.

The adult patients will be asked to donate up to 50mL venous blood samples (schedule seen in 5.1.2.2) from which we will isolate the plasma and mononuclear cells using density gradient centrifugation. This arm of the study will not be recruiting paediatric patients

Samples will be analysed as follows:

- a. Whole blood (including PBMCs post isolation) samples will be analysed for the presence of T-cell populations and subpopulations, cell surface and intracellular immune markers using Mass Cytometry using Time of Flight technology (CyTOF) and/or Flow cytometry
- b. Whole blood samples and PBMCs (isolated from whole blood) will be analysed for the presence of cytokines using CyTOF
- c. Plasma will be used for cytokine analysis using cytokine arrays and ELISA techniques
- d. Serum will be used to determine the presence of autoantibodies utilising protein array technology and ELISA techniques
- e. Transcriptomic analysis
- f. HLA typing

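### The oncology control criteria in 4.1.2 accept any oncological treatment and so do not enforce the same-drug control group that 2.4.1.2 describes

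*Protocol*

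**What the plan says.** Protocol 2.4.1.2 (Control Group) sets the design of the oncology case-control study: "Cases and controls will be recruited in a 1:1 manner", and "Only one group of controls (patients receiving the drug but not exhibiting toxicity) will be recruited for this section". Section 3.6 sets the initial recruitment aim for immunotherapy patients by agent: "25 cases and 25 controls per drug to the case-control study". Section 5.1 describes the immunotherapy controls as patients who tolerate the drug, and adds: "Patients receiving PD-1 inhibitor monotherapy or in combination with a CTLA-4 will be recruited into the study". The control visit schedule in Appendix 3 provides for later samples even where the CPI has been stopped for a reason other than toxicity, so it takes for granted that a control has had a CPI.

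Section 4.1.2 holds the criteria against which a control is screened. Criterion b: "Currently taking oncological treatments without AE (grade 1 toxicity is acceptable". Criterion c, the alternative: "Previously received oncological treatment, did not have >grade one toxicity and have stopped for reasons other than toxicity". On matching: "Controls will be matched for age and duration of treatment to cases", with ethnicity added as criterion d. Case criterion d in the same section states that oncological treatment includes CPIs, targeted treatments and chemotherapy, alone or in combination.

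For the non-oncology arm, 4.1.1 words the corresponding criterion differently: "Currently taking the drug in question without adverse reactions (Control group 1".

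**The concern.** The oncology arm looks for immune features that separate patients with immune-related adverse events (irAEs) from patients without them: T-cell subsets, cytokines and autoantibodies. Section 2.4.2.2 explains that immunotherapies act by upregulating the immune system. Exposure to one may therefore shift the measured markers whether or not toxicity follows. Comparing cases with toxicity-free patients on the same drug removes that effect; comparing them with patients on another class does not.

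The eligibility list is what a recruiting team applies, and recruitment is both local and national. If the list leaves out the drug, the same-drug design depends on each team carrying the restriction over from 2.4.1.2. An analysis restricted to within-drug comparisons could drop off-class controls later, but it could not replace them with same-drug controls who were never recruited.

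**Working it through.** The protocol gives no power, effect size or standard deviation behind the 25 and 25, so there is no figure to reproduce. The check is mainly a comparison of texts.

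**Step 1. What each section requires of an oncology control.**

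| Section | Requirement on treatment | Tied to the drug? |
|---|---|---|
| 2.4.1.2 | Receiving the drug, no toxicity | Yes |
| 3.6 | Controls counted per drug | By implication: it gives a count and does not say what a control receives |
| 5.1 | Tolerant to the drug | Yes |
| Appendix 3, Controls | CPI may have been discontinued | Presumes a CPI |
| 4.1.2, criterion b | Currently on oncological treatments | No |
| 4.1.2, criterion c | Previously had oncological treatment | No |
| 4.1.2, matching | Age, treatment duration, ethnicity | No |
| 4.1.1, Control group 1 (non-oncology) | Taking the drug in question | Yes |

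**Step 2. How wide the term is.** The list naming CPIs, targeted treatments and chemotherapy stands in case criterion d. It reaches the controls because criteria b and c use the same term, in the same section, without narrowing it.

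**Step 3. A test patient.** Take a CPI case and a candidate control who has had chemotherapy only, has had no toxicity above grade 1, is willing and consents, and matches on age, treatment duration and ethnicity.

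- Under 4.1.2 the candidate meets b (or c, if treatment has ended for another reason) and the matching rules. No exclusion refers to the drug; the three exclusions are unwillingness, inability to consent, and the investigator's view that the person is unsuitable.
- Under 2.4.1.2 the candidate fails, because the candidate is not receiving the case's drug.
- Under 3.6 the candidate cannot sensibly count among the 25 controls for that inhibitor.

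The two definitions give opposite answers for the same person.

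**Step 4. A second mismatch.** Criterion c admits patients who have stopped treatment, whereas 2.4.1.2 speaks only of patients receiving the drug. Appendix 3 allows controls to continue after the CPI has stopped. So 4.1.2 and 2.4.1.2 differ on timing as well as on the drug.

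**Step 5. Size of the bias, under stated assumptions.** Let a marker be unrelated to irAEs but differ by δ (in SD units) between drug classes, and let a fraction f of controls be on another class, with all cases on the CPI. The expected case-control difference is

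bias = f × δ.

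With δ = 1 this is 0.1, 0.3 and 0.5 SD for f = 10%, 30% and 50%. It does not shrink as the sample grows. A simulation of 25 v 25 with a two-sided 5% two-sample t-test (200,000 replicates per setting) gave these rejection rates, where 5% is the nominal level:

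| f | δ = 0.5 SD | δ = 1 SD |
|---|---|---|
| 0% | 5% | 5% |
| 10% | 5% | 6% |
| 30% | 8% | 17% |
| 50% | 14% | 37% |

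The class effect, the share of off-class controls and the test are all assumptions; the protocol gives none of them. The table shows only how the error depends on the share of off-class controls.

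**The case against.** The strongest reply is that the protocol, read as a whole, already forbids the off-drug comparison. The 1:1 rule stands in 2.4.1.2, and the next bullet there limits controls to patients receiving the drug. Sections 3.6 and 5.1 and Appendix 3 all point the same way. On this view 4.1.2 merely fails to repeat a restriction made elsewhere, and sites will recruit same-drug controls.

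Much of this stands. A reader might infer from 4.1.2 that the sponsor chose unexposed controls, or that a CPI case and a chemotherapy control are a valid pair under the protocol. Neither follows, because the pairing rule comes from the section that bars that pairing. The shares of 30% and 50% in the table would also require recruiters to disregard several other sections, and at 10% the inflation is negligible.

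The reply does not remove the inconsistency. Criteria b and c do more than leave the drug out: they state a different and wider condition, where 4.1.1 shows that the sponsor can write the narrower one.

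A reader might also infer that 5.1 confines this arm to PD-1 inhibitors with or without a CTLA-4 agent, in flat contradiction of 4.1.2. The text does not go that far. That paragraph concerns patients on immunotherapies and says that such patients will be recruited, not that only they will be. How it relates to the wider scope in 4.1.2 is unclear and needs a sentence, but it is not a proven contradiction.

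Finally, whether cases and controls are analysed only within drug can be left to the statistical analysis plan. Its absence here is not a fault.

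**Conclusion.** The point holds as an inconsistency between the eligibility list and the stated design. Criteria b and c in 4.1.2, with matching that leaves out the drug, admit controls whom 2.4.1.2 excludes and who do not fit 3.6, 5.1 or Appendix 3. The same-drug intention is clear; the criteria used for screening do not enforce it.

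The consequence is confounding of drug exposure with toxicity for whatever share of controls is off-class. The protocol does not allow that share, or the class effect, to be estimated. Under the assumptions above the effect is negligible at a 10% share and material at 30% or more if the class effect is about 1 SD. It is worth correcting because the wording change is easy and a control recruited on the wrong drug cannot be put right in the analysis.

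**What to change.** Amend the protocol in four places.

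1. In 4.1.2, word control criteria b and c as currently taking, or having previously received, the same drug or regimen as the index case, in line with 4.1.1. State whether the match is on the agent or the regimen.
2. In 4.1.2, add the drug or regimen to the matching factors.
3. In 2.4.1.2, extend the control description to previously treated patients, so that it agrees with criterion c and with Appendix 3.
4. In 5.1, say how the sentence on PD-1 and CTLA-4 treatment relates to the wider range of treatments in 4.1.2, case criterion d.

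This is a change of eligibility wording by amendment. Its cost is a smaller pool of controls for rarely used agents, where matching on drug as well as age, duration and ethnicity will be harder.
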